11.9 Follow-up Period

Patients evaluable for the primary outcome will be followed for progression and survival and data recorded by the study team.

11.10 Early Withdrawal of Subject(s)

11.10.1 Criteria for Early Withdrawal

Subjects may voluntarily withdraw from the study at any time. The PI may also withdraw a subject from the study at any time based on his/her discretion. Reasons for withdrawal may include at the PI’s discretion may include, but are not limited to, the following:

- Progressive disease as documented by MRI or physical examination at any time after the initiation of immunotherapy
- Development of unacceptable toxicity
- Pregnancy
- Patients requiring an increase in corticosteroids, with the exception of nasal or inhaled steroid, such that at the time of first vaccination they require a dose above immune suppressive levels, will be removed from the study and replaced. For the purposes of this study, immune suppressive dose will be defined as ≤4 mg of dexamethasone / day or equivalent. Once vaccinations have been initiated, if patients subsequently require increased steroids, they will still be permitted to remain on the study, but every effort will be made to minimize steroid requirements
- Abnormal laboratory values
- Upon request of the subject
- If, in the investigator’s medical judgment, further participation would be injurious to the subject’s health or wellbeing
- Development of intolerable symptoms
- Protocol deviation
- Administrative reasons, such as a major violation of the clinical trial protocol
- Non-compliance of the subject
- Clinical decline
- Allergic or hypersensitivity reaction to Td vaccine
- Allergic or hypersensitivity reaction to PEP-CMV
- Failure to tolerate TMZ therapy for any reason
- Development of any of the following co-morbidities:
 - Unstable angina and/or congestive heart failure requiring hospitalization.

- Transmural myocardial infarction within the last 6 months.
- Hepatic insufficiency resulting in clinical jaundice and/or coagulation defects; note, however, that laboratory tests for liver function and coagulation parameters are not required for entry into this protocol.
- Acquired Immune Deficiency Syndrome (AIDS) based upon current CDC definition; note, however, that HIV testing is not required for entry into this protocol. The need to exclude patients with AIDS from this protocol is necessary because the treatments involved in this protocol may be significantly immunosuppressive.
- Major medical illnesses or psychiatric impairments that in the investigator's opinion will prevent administration or completion of protocol therapy.

11.10.2 Follow-up Requirements for Early Withdrawal

Subjects that are withdrawn by the PI prior to randomization will be considered eligibility failures and thus not followed for survival.

Randomized subjects treated on this study that are withdrawn by the PI for any of the aforementioned reasons after the immune monitoring post-vaccine 3 will continue to be followed for progression and survival by the study team until death or are lost to follow up unless the subject voluntarily withdrew permission to follow for survival.

Randomized subjects that withdraw before the immune monitoring post-vaccine 3 will be followed for survival by the study team unless permission to do so has been withdrawn.

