Patients who receive more than 1 cycle of TMZ will be vaccinated in conjunction with each **subsequent** 28-day TMZ cycle for a total of 6 to 12 cycles of TMZ after RT followed by further vaccination up to 20 vaccines. Patients who receive only 1 cycle of TMZ will be vaccinated on a 28-day cycle with up to 20 vaccines. All cycles, with or without TMZ, may be given every 4 (+ 2) weeks, in order to adjust for slight delays on startup of each 28-day cycle, and the total number of cycles are given at the discretion of the treating oncologist. During vaccine (+/- TMZ) cycles, vaccinations will occur on day 23 (-1 day, + 2 days) of each cycle for each arm: (Arm 1) standard TMZ (150-200 mg/m²/day on days 1-5 of each 28-day cycle), or (Arm 2) dose-intensified TMZ (75-100 mg/m²/day on days 1-21 of each 28-day cycle). All vaccines will be given i.d. approximately 10 cm below the inguinal ligament bilaterally. A target of six cycles with a maximum of twelve cycles of TMZ may be given to patients enrolled prior to approval of protocol version 20181218 and those with MGMT/inconclusive methylation status if enrolled after approval of protocol version 20181218, at the discretion of the treating neuro-oncologist. After the completion of a patient's TMZ cycles, vaccines will continue to be administered every 4 (+ 2) weeks for a maximum of 20 vaccines (unless tumor progression occurs).

Patients will be imaged with contrast-enhanced MRI after vaccine 3 (at cycle 2 initiation visit) and then approximately every 8 weeks [every 2 cycles thereafter (i.e., end of cycles 3, 5, 7, 9, 11)]. RANO criteria [111] will be used for assessment of pseudoprogression and patients demonstrating definitive progression will be removed from study. Any patient removed prior to immune monitoring post vaccine 3 will be replaced for immunologic endpoints. Clinical endpoint comparisons will be made amongst patients randomized to adjuvant TMZ treatment arms who have received at least one vaccine.

Blood for immune monitoring will be obtained:

- Prior to Td pre-conditioning
- During vaccines 1 and 2 (just prior to Component A, 1 and 2 hours after Component A)
- Prior to vaccine 3
- After vaccine 3 (within 2 weeks of vaccine 3 [+ 3 days])
- Prior to vaccines 4 and 6
- At tumor progression (if feasible)

Patients seen by the Duke neuro-oncology team between these vaccine visits may have blood drawn for immune monitoring at the discretion of the study team.

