11.8 Definition of Evaluable Subjects, On Study, and End of Study

Subjects evaluable for the analysis of the primary endpoints will include all randomized patients who undergo immune monitoring post vaccine #3, prior to 2nd vaccine/TMZ cycle. Survival analyses will include all randomized patients evaluable for the primary outcome.

Safety analyses will include all patients who receive vaccine treatment.

Once the patient signs an ICF, that subject will be considered “on study”. Rationale for taking patient off protocol treatment (see Section 11.10.1 below) will be documented.

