15.4.4 Other Exploratory Analyses

Progression-Free Survival and Overall Survival: The Kaplan-Meier estimator will be used to describe the progression-free survival (PFS) and overall survival (OS) experience of patients in each treatment group. These analyses will focus on those patients who have received at least 3 vaccines. PFS is defined as the time between the third vaccine and first documentation of death or disease progression/recurrence. Patients remaining alive without disease progression will have PFS censored at their last follow-up. OS is defined as time between the third vaccine and death. It should be noted that these analyses will focus on only those patients who received Component A alone as we have with other analyses. Additional analyses will describe OS and PFS from randomization.

Radiographic Response: Among the subset of patients with residual disease, the proportion of patients with radiographic response will be estimated with 95% confidence interval.

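### Progression is collected only for patients who reach the post-vaccine-3 draw, which does not support the wider of the plan's conflicting PFS populations

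*Combined protocol and SAP*

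**What the plan says.** Follow-up has two tiers. Section 11.9 says "Patients evaluable for the primary outcome will be followed for progression and survival". Under Section 11.8, being evaluable means being randomised and having the immune-monitoring draw after vaccine 3. Section 11.10.2 adds that treated, randomised patients withdrawn "after the immune monitoring post-vaccine 3 will continue to be followed for progression and survival by the study team until death" or loss to follow-up, but "Randomized subjects that withdraw before the immune monitoring post-vaccine 3 will be followed for survival by the study team", unless permission is withdrawn. Progression is named in the first group and not in the second. Section 11.10.4 defines off study only for evaluable patients.

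The analysis side is less settled:

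- Section 11.8: "Survival analyses will include all randomized patients evaluable for the primary outcome".
- Section 15.4.4, main PFS and OS description, timed from vaccine 3: "These analyses will focus on those patients who have received at least 3 vaccines".
- Section 11.1, with a near-identical sentence in the synopsis: "Clinical endpoint comparisons will be made amongst patients randomized to adjuvant TMZ treatment arms who have received at least one vaccine".
- Section 15.4.4, supplementary: "Additional analyses will describe OS and PFS from randomization". No population is given.

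Section 11.10.3 replaces patients who leave before the draw but keeps their data for whichever analyses are appropriate, without naming them. Section 15.4.4 censors PFS for patients alive without progression at the last follow-up, not at the last progression assessment.

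**The concern.** A PFS analysis needs progression to be looked for, and recorded in the same way, in everyone it includes. Here the rule for who is followed for progression was written around the immune endpoint, while some PFS analyses reach beyond that group. A patient who stops after vaccine 1 or 2 for a reason other than progression counts in the at-least-one-vaccine comparison, yet the protocol does not ask anyone to record when that patient later progresses.

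The censoring rule adds to the problem. If a survival contact counts as follow-up, a patient who progressed months earlier, unrecorded, can be carried as progression-free up to that contact.

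The exit reasons in Section 11.10.1 include clinical decline, toxicity, intolerable symptoms and failure to tolerate TMZ. TMZ schedule is the randomised factor, so early exit could differ between the 5-day and 21-day arms and distort the arm comparison. Section 8.1 expects PFS and OS to inform on the two regimens, so the curves will be read side by side even though no formal test is planned in Section 15.4.4.

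**Working it through.** The plan states no PFS sample size, event target or power, so there is no figure to reproduce. The main check sets collection against analysis.

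**1. Does collection support each population?**

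| Source | Population | Time origin | Progression collected under 11.9 and 11.10.2? |
|---|---|---|---|
| 11.8 | Randomised, had the post-vaccine-3 draw | Not stated | Yes, for all |
| 15.4.4, main | At least 3 vaccines, Component A only | Vaccine 3 | Yes, except for a patient who leaves between vaccine 3 and the draw (a window of 2 weeks, +3 days) |
| Synopsis, 11.1 | Randomised, at least 1 vaccine | Not stated | No for patients who leave after vaccine 1 or 2, or after vaccine 3 but before the draw |
| 15.4.4, additional | Not stated | Randomisation | If all randomised: no for any early leaver, including those who leave before vaccine 1 |

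The first row assumes that survival analyses in 11.8 covers PFS.

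**2. Which events are lost?** Progression is itself a withdrawal reason in 11.10.1, documented by MRI or examination, so a patient who leaves because of progression has the event on record. The loss is confined to later progression in patients who left early for another reason.

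**3. Which way does the error run?**
- Counted only at death: death follows progression, so PFS is too long.
- Censored at a later survival contact after an unrecorded progression: PFS is too long.
- Censored at exit: direction uncertain. Leavers in clinical decline probably have worse prognosis. Sections 11.5.1 and 14.2.1 suggest that vaccine reactions may accompany clinical response; if so, leavers for toxicity may do better.

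**4. How many early leavers?** Section 15.1 reports that, as of 20200110, 15 patients had received Component A only and 8 were evaluable. The other 15 − 8 = 7 (7/15 = 47%) may include patients still on their way to the draw. So 47% is an upper bound on early leavers among those 15 vaccinated patients, not a dropout rate, and it does not count randomised patients who left before vaccine 1.

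**5. Illustrations of size.** Both use a true median PFS of 6.7 months (historical controls, Section 9.7), exponential times, and lost progressions counted at death.

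*Model A.* No leaver's progression is recorded; death has a median of 15 months (Section 9.1 says most patients live less than this from diagnosis). With leaver fraction p, the apparent median t solves (1 − p)·2^(−t/6.7) + p·2^(−t/15) = 0.5.
- p = 0.2: t = 7.72 (check: 0.8 × 0.450 + 0.2 × 0.700 = 0.50)
- p = 0.3: t = 8.33
- p = 0.4: t = 9.01

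*Model B.* Time from progression to death has a median of 8 months (an assumption, not in the documents). With leaver fraction q and a fraction f of their progressions recorded, the share affected is m = q(1 − f). With a = ln2/6.7 and b = ln2/8, the apparent median solves (1 − m)·e^(−at) + m·[b·e^(−at) − a·e^(−bt)]/(b − a) = 0.5. Simulated medians in months:

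| q | f = 0 | f = 0.5 | f = 1 |
|---|---|---|---|
| 10% | 7.5 | 7.1 | 6.7 |
| 25% | 8.8 | 7.7 | 6.7 |
| 47% | 11.2 | 8.7 | 6.7 |

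Check at q = 25%, f = 0, t = 8.8: 0.75 × 0.402 + 0.25 × 0.797 = 0.50. Starting from 15.4 months (the PFS in Section 7.1), the f = 0 column becomes 16.5, 18.4 and 21.1.

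**6. Difference between arms.** If early exit were 20% in one arm and 40% in the other (a split with no source in the documents), Model A gives 9.01 − 7.72 = 1.3 months between arms with identical true PFS.

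**The case against.** The strongest reply is that the main PFS analysis is largely sound. Section 11.8 limits survival analyses to evaluable patients, exactly the group that Section 11.9 follows for progression. Section 15.4.4 starts the main analysis at vaccine 3 and requires three vaccines, so nearly all early leavers are out. A reader might infer that no PFS population in the plan has its events collected. The documents do not support that, and this part of the reply stands.

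It is also fair that the analysis from randomisation may change only the time origin. With no population stated, it cannot be shown to include early leavers. The at-least-one-vaccine sentence is the only one that clearly does.

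A reader might also infer that early leavers' progressions all go unrecorded, or that PFS is certainly biased upward. Neither follows: progression that causes withdrawal is documented, and censoring at exit has no fixed direction. In addition, Section 11.1 withdraws patients who are unable to tolerate TMZ, or who need steroids above the protocol limit, before vaccination. Those exits affect an all-randomised analysis but not the vaccinated sets.

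Finally, Section 8.2.3 makes PFS exploratory and descriptive. That limits severity but does not reconcile the populations. Section 11.8 does not settle the matter either, because Sections 11.1 and 15.4.4 say something different.

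**Conclusion.** The point holds in a limited form. The plan names conflicting populations for its clinical endpoints, and its progression follow-up supports the narrower ones only. The at-least-one-vaccine comparisons, and PFS from randomisation if it covers all randomised patients, would lack progression events occurring after an early exit for a reason other than progression. Counting those patients at death, or censoring them at a later survival contact, overstates PFS; censoring at exit is potentially informative in an unknown direction. Either effect could differ by TMZ arm.

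The size cannot be fixed from the documents. The f = 0 and Model A figures are worst-case illustrations: they assume that no leaver's progression is recorded, and Model A uses a survival figure dated from diagnosis as if it ran from the start of PFS. The error from this mechanism vanishes if all the progressions are recorded or the early leavers are excluded. It is tempting to read 8 of 15 evaluable as nearly half dropping out, but accrual was continuing and the text says only that 8 were evaluable at that date. Because PFS is exploratory, severity is modest. The change is still worth making while patients are being followed, since progression dates not collected may not be recoverable at analysis.

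**What to change.** 1. Amend Sections 11.9 and 11.10.2 so that every randomised patient, whenever and for whatever reason vaccination stops, is followed for progression (date and basis, taken from standard-of-care MRI and clinic records) and for survival, until death, loss to follow-up or withdrawal of permission. Extend the off-study definition in 11.10.4 to all randomised patients in the same terms.
2. State one population and one time origin for each PFS and OS analysis, and reconcile the synopsis, 11.1, 11.8 and 15.4.4. Say explicitly who is in the analysis from randomisation, and which analyses 11.10.3 regards as appropriate for replaced patients.
3. In 15.4.4, censor PFS at the last progression assessment rather than the last follow-up.

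If the sponsor prefers to drop the wider PFS analyses, item 2 removes most of the mismatch; item 1 is needed if they are kept. The cost is protocol wording plus a small amount of record abstraction and data entry for early leavers. No study scan or visit is added.

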11.10.3 Replacement of Early Withdrawal(s)

Subjects who voluntarily withdraw prematurely or who are withdrawn by the PI prior to immune monitoring post vaccine #3 will be replaced. However, the data from these patients will be included in all appropriate analyses.

11.10.4 Off Study

Subjects evaluable for the primary outcome are considered off study if lost to follow up or deceased.

12 DESCRIPTION OF STUDY EVALUATIONS

12.1 Schedule of Events

Table 3: Schedule of Events

	Pre-XRT/TMZ Screening ⁵	Post-XRT/TMZ screening ⁶	TMZ Cycle 1 ⁷	Td pre-conditioning ⁸	Vaccines 2 & 3	TMZ Cycles 2-12 ⁹	Vaccines 4-20 ¹⁰	Progression
CMV consent, if needed	X	X						
Main study consent		X						
Td booster		X						
Medical History		X						
History and Physical		X		X	X		X	
Neurological Exam		X		X	X		X	
KPS		X		X	X		X	
Curran		X						
CMV screen	X	X						
MGMT methylation		X						
CBC w/ differential ¹¹		X	X	X	X	X	X	
CMP ¹¹		X	X	X	X	X	X	
Beta HCG (quantitative)		X						
Cortisol Levels ¹¹		X	X		X		X	

⁵ If patients have yet to undergo XRT/TMZ when they are presented with the study, they will undergo the pre-XRT/TMZ screening. If the patient is CMV positive, they will undergo standard of care XRT/TMZ and then return post XRT/TMZ for the next screening portion. If patients have already been tested for CMV, they will not need to sign the CMV consent or have the CMV test repeated.

⁶ If patients have already undergone XRT/TMZ when they are presented with the study, they will undergo both pre- and post-XRT/TMZ screening after completing XRT/TMZ, prior to Cycle 1 of adjuvant TMZ. If patients have already been tested for CMV, they will not need to sign the CMV consent or have the CMV test repeated.

⁷ Temodar cycle 1 should start 2-6 weeks post the end of XRT/TMZ and will last until 2 weeks post Vaccine #3. Patients will only take either 5 days of Temodar on days 1-5 (Arm 1) or 21 days on days 1-21 (Arm 2) based on the randomization results.

⁸ Td pre-conditioning occurs on day 22 (+1 day) and is given in the RIGHT groin for all patients. Vaccine #1 is given on day 23 (+2 days).

⁹ Temodar cycles 2 – 12, if applicable, are 28-day cycles (Patients who enrolled prior to approval of protocol version 20181217 and patients who enrolled after approval of protocol version 20181218 who are MGMT-methylated. Cycles may be given every 4 (+2) weeks, in order to adjust for slight delays on startup of each 28-day cycle, and the total number of cycles are given at the discretion of the treating oncologist.

¹⁰ Vaccines #4 - #20 will be given every 4-6 weeks or on day 23 (-1 day/+2 days) of each TMZ cycle depending on MGMT methylation status.

¹¹ CBC w/diff and CMP to be drawn at post XRT/TMZ screening, days 14, 21, and 28 (+/- 2 days) of each TMZ cycle, and at the discretion of the treating oncologist.

¹¹ At post-XRT/TMZ screening for baseline and prior to each vaccine.

	Pre-XRT/TMZ Screening ⁵	Post-XRT/TMZ screening ⁶	TMZ Cycle 1 ⁷	Td pre-conditioning ⁸	Vaccines 2 & 3	TMZ Cycles 2-12 ⁹	Vaccines 4-20 ¹⁰	Progression
Immune Monitoring			X ¹³	X ¹⁴	X ¹³	X ¹⁵	X ¹⁶	X ¹⁷
Vaccine				X	X		X	
Vitals ¹⁸	X		X	X	X		X	
Randomization		X						
MRI		X				X ¹⁹	X ²⁰	
Pathology testing ²¹		X						X ¹⁷
Adverse Events ²²					Ongoing			
Con Meds ²²					Ongoing			

12.2 Medical History

The medical history is to include any current active diagnoses and any previously treated illnesses, including the approximate date of onset (at minimum indicate the year or approximate year) and date of resolution if applicable, and description of any prior surgeries. The body systems to be reviewed and any concurrent or past diagnoses documented include but are not limited to: eyes, ears, nose, and throat; respiratory; cardiovascular; gastrointestinal; musculoskeletal; neurological; endocrine/metabolic; hematologic/lymphatic; dermatological; genitourinary; psychiatric and allergies. In addition, the patient's date of birth, gender, race, and ethnicity should be documented. If serum CMV testing was not done and/or results are not available, a screening consent will be obtained and CMV testing will be performed.

12.3 Physical and Neurological Examination

Physical examinations are to be completed by the investigator or designated participating clinician. The minimum body systems to be examined for any abnormalities and symptoms include: general appearance; skin; lymphatic; head, eyes, ears, nose, throat; extremities; respiratory; cardiovascular; abdominal; musculoskeletal; neurological and genitourinary.

General neurological assessments are to be completed by the investigator or designated participating clinician. The assessment includes but is not limited to: a general

¹³ During vaccine 1: just prior to Component A, 1 and 2 hours after Component A (~20 mL, 1 EDTA lavender top tube and 1 serum red top tube at each blood draw). Just prior to vaccine 2 (1 EDTA lavender top tube, 1 serum red top tube, and 6 yellow ACD tubes). During vaccine 2: 1 and 2 hours after Component A (~20 mL, 1 EDTA lavender top tube and 1 serum red top tube at each blood draw). Just prior to vaccine 3 (9 yellow ACD tubes).

¹⁴ Prior to Td pre-conditioning (~90 mL, 9 yellow ACD tubes and 2 red serum tubes)

¹⁵ At the clinic visit 2 weeks after vaccine 3 [+3 days] (~90 mL, 9 yellow ACD tubes and 2 red serum tubes)

¹⁶ Prior to vaccines #4 and #6 (~90 mL, 9 yellow ACD tubes and 2 red serum tubes)

¹⁷ Immune monitoring blood and pathology testing performed at progression, if possible

¹⁸ Vital signs will be measured at all protocol-indicated visits before and approximately every 30 minutes after vaccination during the post-vaccine monitoring times described in Sections 11.4.2 and 12.6, until discharged from the clinic. Measurements to be reported include temperature in Celsius or Fahrenheit, pulse (beats per minute), respiratory rate (breaths per minute) and blood pressure.

¹⁹ MRI at prior to TMZ cycle 2 clinic visit (within 2 weeks +3 days after vaccine 3)

²⁰ MRI visits take place at the vaccine visit that coincides with the end of TMZ/vaccine cycles 1, 3, 5, 7, 9, 11 and then after every other vaccine visit during the post-TMZ period.

²¹ Pathology testing is performed per BTC standard of care practice and is obtained at the time of new patient evaluation

²² Adverse events and con meds will be collected throughout the study starting with the post-XRT/TMZ screening visit.

mental status examination (orientation, memory, attention/concentration, and language), assessment of cranial nerves, motor, coordination and gait, reflexes, and sensory evaluation.

